Final

Clinical Evaluation of clariti Monthly Multifocal and clariti® 1 day Multifocal

Sponsor Study Code: EX-MKTG-136

Protocol Date: April 23, 2022

Sponsor Company: CooperVision, Inc.

Document Type: Protocol

Study Category: Post Market

Start Date: May 2022
Finish Date: July 2022

Clinical Site: School of Optometry Clinic, National

Autonomous University (UNAM), Mexico City

Revision History

Document number	Date	Comments
EX-MKTG-136	4/15/2022	First draft (v 1.0)
EX-MKTG-136	4/22/2022	FINAL
EX-MKTG-136	4/23/2022	FINAL UPDATED

PERSONNEL & FACILITTIES

Protocol Synopsis

Protocol Number	EX-MKTG-136
Title	Clinical Evaluation of clariti Monthly Multifocal and clariti® 1 day Multifocal.
Name of Device(s) and (by USAN material)	Clariti Monthly Multifocal (somofilcon A), clariti 1-Day Multifocal (somofilcon A)
Indications for Use	Approved for use:
Study Design	Single-blind, (participant masked), interventional, prospective, direct refit, bilateral wear study.
Purpose	The aim of this non-dispensing fitting study is to evaluate the short term lens fit, vision performance and patient subjective experiences of the Clariti Monthly Multifocal when compared to the Clariti 1-Day Multifocal after 15 minutes of daily wear.
Study Duration	 The anticipated timeline for this study is as follows: Patient enrolment and completion: May 3 - June 17, 2022 Visits: V1: (BL/trial fit/lens order), V2: Dispense / evaluate P1 V3: 15 minutes. Evaluate P1/Dispense P2. V4: 15 minutes. Evaluate P2 / study exit
Patient Population	Habitual soft contact lens wearers who currently wear multifocal contact lenses, sphere contact lenses for monovision, or use spectacles for near vision correction, that provide written informed consent and meet the protocol entrance criteria.
Sample Size	Target enrollment and completion is 40 subjects.
Center Destination (Mexico)	School of Optometry Clinic, National Autonomous University (UNAM)
Number of Centers	Single Center
Patient Follow-up	Subjects enrolled in this study will be followed up after the lens dispensing session: • Post dispensing follow-up at 15 minutes for each study lens pair
Primary Endpoint	Subjective comfort on insertion. Subjective handling (insertion & removal)

Table of Contents

1	lı	ntro	duction6					
2	S	Study	y Objective6					
3	S	Study	y Hypothesis7					
	3.1	5	Study Hypothesis7					
4	S	Study Design7						
5	lı	nves	tigational Sites7					
	5.1	١	Number of Sites7					
	5.2	I	nvestigator Recruitment7					

Soft multifocal contact lenses, (MFCLs), are a great option for new and established presbyopes, offering good vision performance with the added benefit of improved cosmesis and convenience compared to spectacles, and provide them the flexibility to change-up their vision correction. CL manufacturers are continually innovating in this area, with the increased availability of soft MFCLs with novel designs in a range of replacement frequencies from daily disposable to monthly replacement, and different materials including silicone hydrogels.

Therefore, CooperVision is interested in comparing the short-term clinical performance and subjective acceptance of Clariti Monthly Multifocal, (**LENS A**), to the Clariti 1-Day Multifocal, (**LENS B**), silicone hydrogel contact lenses. A non-dispensing fitting study is proposed to evaluate the short-term clinical performance of these lenses.

2 Study Objective

The aim of this non-dispensing fitting study is to evaluate the short term lens fit, vision performance and patient subjective experiences of the Clariti Monthly Multifocal when compared to the Clariti 1-Day Multifocal after 15 minutes of daily wear.

The primary outcome variable is:

Subjective comfort ratings on insertion (assessed by subjects)

3.1 Study Hypothesis

- Null hypothesis (Ho): There is no difference in clinical performance and subjective assessments between multifocal lens types.
- Alternative hypothesis (H1): There is a difference in clinical performance and subjective assessments between multifocal lens types.

4 Study Design

This is a 40-subject, single-blind, (participant masked), interventional, prospective, direct refit, bilateral wear study. It is anticipated that this study will involve 4 visits as follows: **V1**: (BL/trial fit/lens order), **V2**: Dispense / evaluate P1. **V3**: 15 minutes. Evaluate P1/Dispense P2. **V4**: 15 minutes. Evaluate P2 / study exit.

5 Investigational Sites

5.1 Number of Sites

This will be a single center investigational site in Mexico City. (Target 40 subjects).

5.2 Investigator Recruitment

This study will be conducted at School of Optometry Clinic; National Autonomous University (UNAM) Mexico City. The Investigators will be required to fulfil the following criteria:

- Licensed optometrist with at least two years of contact lens fitting experience.
- Experienced Investigators who will be trained in Good Clinical Practice (GCP) by the principal investigator.
- In-office email or fax.
- Willingness to follow the study protocol and to co-operate with the study monitors.

This clinical study is designed to be in conformance with the ethical principles in the Declaration of Helsinki, with the ICH guidelines for Good Clinical Practice (GCP) and all the applicable local guidelines.

6.1 Relevant Standards / Guidelines

This implementation document has been developed in accordance with the following:

- ISO 14155. Clinical Investigation of Medical Devices
- ICH Harmonized Tripartite Guideline for Good Clinical Practice
- Declaration of Helsinki

6.2 Institutional Review Board

This study will be conducted in accordance with Institutional Review Board regulations (U.S. 21CFR Part 56.103) or applicable IEC regulations. Copies of all IRB/IEC correspondence with the investigator/sponsor will be kept on file. The study will commence upon approval from the following Ethics Committee: Comisión de Ética de la FESI. [name]. [contact] and email address [contact].

6.3 Clinical Trial Registration

This study will be registered with clinical trials.gov in accordance with section 801 of the Food and Drug Administration (FDA) Act which mandates the registration of certain clinical trials of drugs and medical devices.

6.4 Informed Consent

Informed consent, (Appendix 1), shall be obtained in writing from the subject and the process shall be documented before any procedure specific to the clinical investigation is carried out.

7 Potential Risks and Benefits to Human Subjects

There may be direct benefits to the subjects in this study such as improved vision, comfort, convenience, and cosmetic advantage. Participation in a study may contribute to scientific research information that may be used in the development of new contact lens products. In addition, subjects will receive an examination of the front part of their eyes and may have the opportunity to try a different type of soft contact lenses and/or different lens care products at no cost to them. The contact lens materials used in this study are commercially available intended for daily wear (NOT extended wear) similar to the average wearing time of 10-16 hours for daily wear lenses.

This study is considered to be a non-significant risk study based on United State Food and Drug administration (FDA) and International Standards Organization (ISO) guidelines because the study devices used as intended in this study (daily wear) don't represent a potential for serious risk to the health, safety or welfare of the subject, and (2) it is not an implant, (3) it is not used to support or sustain human life, (4) it is not of substantial importance in diagnosing, curing, mitigating or treating disease or otherwise prevents impairment of human health, (5) does not present a potential for serious risk to the health, safety or welfare of the subject.

Complications that may occur during the wearing of contact lenses include discomfort, dryness, aching or itching eyes, excessive tearing, discharge, hyperemia and variable or blurred vision. More serious risks may include photophobia, iritis, corneal edema or eye infection. Although contact lens-related infections are very infrequent, the possibility does exist. The incidence of infection due to day-wear soft lenses is 0.035%. Almost always an infection will occur only in one eye. This risk is assumed by 35-million Americans who currently wear contact lenses. Routine clinical procedures including auto-refraction, auto-keratometry, visual acuity, anterior ocular health assessment, and contact lens fitting will be used. In addition, high magnification imaging of the lens fit may be made using 35 mm or digital cameras, in vivo confocal microscopy, and/or specular microscopy. Patients will be monitored in the clinic during the study to reduce if not eliminate the occurrence of adverse or potential adverse events. Patients will be given instructions from the study investigator regarding early symptoms and signs of adverse events and their contact information.

8 Materials and Methods

8.1 Participants

Habitual soft contact lens wearers who currently wear multifocal contact lenses, sphere lenses for monovision, or sphere lenses for distance vision correction and use spectacles for near vision correction, that provide written informed consent and meet the protocol entrance criteria. Subjects will be recruited from the National Autonomous University School of Optometry databases who agree to voluntarily participate in the study (Appendix 2, timeline). All subjects will be screened to determine study eligibility. Each subject will be given a unique ID number. Additionally, all subjects must meet the study inclusion and exclusion criteria listed below.

Inclusion criteria

A person is eligible for inclusion in the study if he/she:

- 1. Is at least 42 years of age and has full legal capacity to volunteer.
- 2. Has read and signed an information consent letter.
- 3. Self-reports having a full eye examination in the previous two years.
- 4. Anticipates being able to wear the study lenses for at least 8 hours a day, 5 days a week.
- 5. Is willing and able to follow instructions and maintain the appointment schedule.
- 6. Habitually wears multifocal soft contact lenses, or sphere lenses for monovision, or sphere lenses for monovision, or sphere lenses for distance vision correction and use spectacles for near vision correction, for the past 3 months minimum.
- 7. Has refractive astigmatism no higher than -0.75DC.
- 8. Is presbyopic and requires a reading addition of at least +0.75D and no more than +2.50D.
- 9. Can be fit and achieve binocular distance vision of at least 20/30 Snellen (or +0.20 logMAR) which participants also deem to be 'acceptable', with the available study lens parameters (powers +4.00 to -6.00DS) (see Table 1).

Exclusion Criteria

A person will be excluded from the study if he/she:

- 1. Is participating in any concurrent clinical or research study.
- 2. Has any known active* ocular disease and/or infection that contraindicates contact lens wear.
- 3. Has a systemic condition that in the opinion of the investigator may affect a study outcome variable.
- 4. Is using any systemic or topical medications that in the opinion of the investigator may affect contact lens wear or a study outcome variable.
- 5. Has known sensitivity to the diagnostic sodium fluorescein used in the study.
- 6. Self-reports as pregnant, lactating or planning a pregnancy at the time of enrolment.
- 7. Has undergone refractive error surgery or intraocular surgery.
- * For the purposes of this study, active ocular disease is defined as infection or inflammation which requires therapeutic treatment. Mild (i.e., not considered clinically relevant) lid abnormalities (blepharitis, meibomian gland dysfunction, papillae), corneal and conjunctival staining and dry eye are not considered active ocular disease. Neovascularization and corneal scars are the result of previous hypoxia, infection or inflammation and are therefore not active.

Age ≥ 42 years is an inclusion criterion because presbyopia is unlikely in persons aged < 42 years and, if present, may not be due solely to presbyopic changes representative of the wider population.

Pregnant and lactating women are not being excluded from the study due to safety concerns but due to fluctuations in refractive error, accommodation and/ or visual acuity that occur secondary to systemic hormonal changes. It has further been shown that pregnancy could impact tear production, which could impact dry eye symptoms. Such fluctuations could affect data, thereby negatively affecting study data integrity.

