8.2 Study Materials

8.2.1 Contact lens

CooperVision will provide the site with an inventory of both study lenses (**LENS A**) and (**LENS B**) to allow participants to be fit with the lens powers available for this study i.e., sphere +4.00D to - 6.00D, in 0.25D steps, in both add powers.

All subjects will be trial fitted and, if suitable, dispensed the first pair of the assigned lens brand assigned per a determined table (Appendix 3). The lenses used in this study are all FDA approved and marketed products. Details of the study contact lenses are shown in Table 1.

Table1: Study lens parameters

Brand	Clariti Monthly Multifocal (LENS A)	Clariti 1-Day Multifocal (LENS B)	
Manufacturer	CooperVision	CooperVision	
Material	somofilcon A	somofilcon A	
FDA Class Group 5		Group 5	
WC %	56%	56%	
Base Curve (mm)	8.6	8.6	
Lens Diameter (mm) 14.1		14.1	
Sphere Power (D) +4.00 to -6.00 (0.25 steps)		+4.00 to -6.00 (0.25 steps)	
Add Power (D) Low, High (see fitting guide)		Low, High (see fitting guide)	
Wearing schedule Daily wear		Daily wear	

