8.2.6 Masking and Control of Study Materials

The contact lenses, (**LENS A**, and **LENS B**), will be masked to the subject only. The lenses will be removed from their blister pack by an assistant and transferred to an unmarked lens case to maintain the participants masked of the study lenses. Participants will then be instructed to remove the lenses from the lens case and insert them onto their eyes. It is not possible for the study investigators to be masked because of the need to follow the specific lens fitting guide during the lens prescription optimization visit.

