APPENDIX 5 - GRADING & MEASUREMENT SYSTEM

Variable	Assessment Method	Grading/Measurement System		
Wearing Times				
Average # of days lenses worn in a week	Enter the number of days lenses are worn during the week.	Days per week		
Average Daily Wearing Time	Typical time of day when lenses inserted and removed.	Time of day to nearest half hour		
Average # of hours of wear per day	Enter the number of hours lenses are worn per day.	Hours per day		
Average Comfortable Wearing Time	Typical time of day when subject first experiences LENS Awareness or irritation.	'Does CL comfort deteriorate during wear?' (tick- box). If yes, record time of day to nearest half hour when first aware of lenses		
Typical Removal Time	Typical time of day when subject removes the lens.	Time of day to nearest half hour		
Subjective	Assessments (Questions asked by t	he investigator and recorded)		
Comfort, dryness, handling, lens fit, vision satisfaction.	Assessed by subject on a 0-10 scale.	0-10 scale Comfort: (10= can't feel) Dryness: (10=no dryness) Handling: (10=very easy) Fit stability (10=very stable) * Vision: (10=very satisfied)		
Vision Quality	Assessed by subject on a 0-10 scale.	Vision quality: (10=Excellent vision, totally sharp)		
Night Vision Quality	Assessed by subject on a 0-10 scale.	Vision quality: (10=Excellent vision, totally sharp)		
Vision Stability	Assessed by subject on a 0-10 scale.	Vision stability: (10=perfectly stable, not fluctuating, changing)		
Satisfaction	Subject's assessment of various symptoms on a 4-point Likert scale.	Completely satisfied Somewhat satisfied Somewhat dissatisfied Completely dissatisfied		
Preference	Subject's preference for one of two contact lenses.	Forced choice: Study lenses or Habitual		
Vision				
Distance VA – High contrast	Measured using Snellen or logMAR chart.	Snellen or logMAR visual acuity (VA) to nearest letter.		
Lens Surface assessed using slit lamp				
Front Surface Wettability	Lens surface viewed with a slit lamp, white diffuse light and broad beam under low-medium magnification.	0 – 4 0=poor 4=excellent		

Variable	Assessment Method	Grading/Measurement System		
	Lens surface deposits assessed us	ing the slit-lamp		

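### Current wearers of either study lens can enrol and the paired analysis ignores habitual lens, so own-lens familiarity could bias the ratings, by an unknown and possibly small amount

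*Combined protocol and SAP*

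**What the plan says.** **Eligibility (section 8.1).** Inclusion 6 accepts a person who "Habitually wears multifocal soft contact lenses, or sphere lenses for monovision", or who wears distance spheres with reading spectacles, for at least the past 3 months. No brand is named. The seven exclusions cover concurrent studies, active ocular disease, systemic conditions, medication, fluorescein sensitivity, pregnancy or lactation, and surgery; the last reads "Has undergone refractive error surgery or intraocular surgery". None concerns current or past wear of LENS A or LENS B.

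**Availability (section 8.2.1).** "The lenses used in this study are all FDA approved and marketed products". Subjects are recruited from the university's School of Optometry databases (section 8.1).

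**Masking (section 8.2.6).** The lenses "will be masked to the subject only". An assistant takes them from the blister pack, and they are "transferred to an unmarked lens case to maintain the participants masked of the study lenses". Subjects then insert the lenses themselves.

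**Outcome and analysis.** Section 2 gives the primary outcome as subject-rated comfort on insertion, and the synopsis adds handling. Section 10.1 compares the lenses with paired tests. It has no covariate, stratum or sensitivity analysis for habitual lens. Appendix 5 grades preference as "Forced choice: Study lenses or Habitual".

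**The concern.** For a subject who already wears LENS A or LENS B, one side of the within-subject comparison is a lens they have handled for at least 3 months, and the other is not. Any rating advantage or disadvantage that comes from this familiarity enters the paired difference as if it were a property of the lens. It attaches to the lens and not to the wearing period, so randomising the order would not remove it (section 8.3 in any case fits LENS A first to everyone).

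Such a subject is also better placed than others to recognise their own lens, since an unmarked case hides the packaging but not the lens. That matters because the participant is the only masked party and supplies the primary outcome.

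One consequence needs no assumption about effect size. The preference item sets study lenses against the habitual lens. When the habitual lens is a study lens, the two options overlap and the answer has no clear meaning, yet section 10.1 would carry it into a chi-square test.

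**Working it through.** **1. The plan's own figure.** Section 10.2 gives a two-sided paired t-test with alpha 0.05, SD of paired differences 2.2, difference 1.0 and N = 40. The noncentrality is (1.0 / 2.2) × √40 = 2.87 on 39 degrees of freedom. Exact power from the noncentral t distribution is 0.8005, against the stated 0.800497. At N = 45 it is 0.8466, against the stated 0.846619. The plan's figures reproduce.

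**2. Form of the bias.** Let pA and pB be the shares of subjects who habitually wear LENS A and LENS B, and d the familiarity effect in points on the 0–10 scale, taken as equal for both. Then:

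- bias in the mean A − B difference = (pA − pB) × d
- if pA = pB, the bias is zero
- if d is near zero, the bias is near zero whatever the shares

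The documents give neither the shares nor d, so every figure in step 3 rests on assumption.

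**3. Illustration.** Take d = 1 point and a net share f made up of wearers of one lens only. The mean shifts by f × d, and the variance of the differences becomes 2.2² + f(1 − f)d².

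| Assumed net share f | Bias (points) | SD of differences | Chance of p ≤ 0.05 with no true difference | Power for a true 1.0 when the bias opposes it |
|---|---|---|---|---|
| 0 | 0 | 2.200 | 5.0% | 80.0% |
| 10% | 0.10 × 1 = 0.1 | √(4.84 + 0.09) = 2.220 | 5.9% | 70.5% |
| 20% | 0.20 × 1 = 0.2 | √(4.84 + 0.16) = 2.236 | 8.6% | 59.7% |

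The standard error of the mean difference is 2.2 / √40 = 0.35, so these shifts are about 0.3 and 0.6 of one standard error.

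**4. Cost of each remedy.**

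- Exclusion at entry: 40 eligible completers still give 80% power. Screening rises to 40 / 0.90 = 44.4, so 45, if 10% are ineligible, or 40 / 0.80 = 50 if 20% are.
- Dropping such subjects in a sensitivity analysis: power for 1.0 point is 75.5% with 36 left (4 removed) and 70.2% with 32 left (8 removed).

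**The case against.** The strongest counter-argument is Table 1. It lists the two lenses with the same manufacturer, material (somofilcon A), water content (56%), base curve (8.6 mm), diameter (14.1 mm), sphere range and add labels. On every listed parameter, a habitual wearer of one is wearing the equivalent of the other. Much of the familiarity may therefore extend to both lenses and cancel in the paired difference, and recognition by feel may be difficult. This stands as a reason to expect a small effect. It does not show that the effect is zero, because Table 1 does not cover everything that a wearer might perceive.

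Three further points limit the concern:

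- Both lenses are trial-fitted and optimised at V1 (section 8.3.1). A reader might infer that the non-habitual lens is met for the first time when it is rated; the visit schedule does not support that.
- Calling the design a "direct refit, bilateral wear study" (section 4), together with the wording of the preference item, suggests that the authors expected the habitual lens to differ from the study lenses. No criterion enforces that expectation.
- Habitual brand may already be recorded. The Appendix 6 forms are not visible, some V1 items are blank in the available text, and the wearing-time items in Appendix 5 look like baseline data on habitual lenses. A missing field cannot be asserted.

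A reader might also infer that the recruitment source makes study-lens wearers common. Section 8.1 names School of Optometry databases, and nothing in the documents gives the use of either lens in that population.

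**Conclusion.** The gap in eligibility and analysis is plain from the text: current wearers of either study lens may enrol, and nothing in section 10.1 deals with them. The preference item is uninterpretable for any who do. Beyond that the concern is conditional. Bias in comfort or handling needs three things together: that such wearers enrol, that familiarity changes their ratings, and that A wearers and B wearers do not offset each other. Its direction is unknown.

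A reader might go further and conclude that the comparison is biased and the mask broken, or that the bias could approach half of the planned difference (for example 30% × 1.5 points = 0.45). The documents do not support either. They give no share and no effect size, the larger figure multiplies two high guesses and ignores offsetting between the groups, and Table 1 points towards a small effect. The 0.1–0.2 points shown above is likewise an illustration and not an estimate.

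This is a low-cost improvement to the design and not a finding that the result would be invalid.

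**What to change.** - Add an eighth exclusion to section 8.1: current habitual wear, or habitual wear within the past 3 months, of Clariti Monthly Multifocal or Clariti 1-Day Multifocal.
- Confirm that the V1 case report form records habitual lens brand, and add the field if it does not.
- If any such subject is already enrolled, state in section 10.1 that the primary paired comparison will be repeated without them as a sensitivity analysis.

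The cost is one criterion, at most one form field, and a slightly narrower recruitment pool. Monovision wearers, distance-lens wearers who use reading spectacles, and wearers of other multifocals stay eligible. The required N and its power do not change; only the screening load or the power of the sensitivity analysis is affected, as set out in step 4 of the working.
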